- 13) Unsupervised Pulmonary Function (FEV₁, PEF) with AM3® device
- 14) Phone call to be made twice a day, ideally at the time of study drug administration ([see section 5.3.6](#)). During the afternoon or evening calls, AEs should be collected in line with a morning call
- 15) Allocation to treatment may be performed at any time following enrolment but must be completed prior to first drug administration. Randomisation not required for CF subjects undergoing second treatment period
- 16) AEs and concomitant therapies will be recorded throughout the trial, but will be specifically asked for at the time points indicated in the [Flow Chart II](#) above including during phone calls when patients are ex clinic.
- 17) Respimat device and AM3® device training initially, then instruction (if required).
- 18) Systolic and diastolic blood pressures (BP) as well as pulse rate (PR) will be measured by a blood pressure monitor at the times indicated in the Flow Chart II, after subjects have rested for at least 5 min in a supine position.
- 19) Includes, urine pregnancy test for females at Screening, Day 1, Day 7, Day 14 and Day 30. Serum pregnancy test at Day -5 to -3, and e.o.s. visit.
- 20) To be measured on home based spirometer (AM3®), prior to drug administration.
- 21) Baseline ECG (Day 1) must be in triplicate. All other ECGs to be single.
- 22) Urine drug screen and alcohol breath test to be performed at both screening and Pre-dose Day 1.,
- 24) Serum electrolytes to be collected using local laboratory values in addition to central laboratory values.
- 25) Planned time is required for technical reasons and the actual dates and times could be between Day -7 to -3.

TABLE OF CONTENTS

| | |
|---|-----------|
| CLINICAL TRIAL PROTOCOL..... | 1 |
| TITLE PAGE | 1 |
| CLINICAL TRIAL PROTOCOL SYNOPSIS | 2 |
| FLOW CHART I – HEALTHY VOLUNTEERS | 5 |
| FLOW CHART II – CF SUBJECTS..... | 8 |
| TABLE OF CONTENTS | 11 |
| ABBREVIATIONS..... | 15 |
| 1. INTRODUCTION..... | 17 |
| 1.1 MEDICAL BACKGROUND | 17 |
| 1.2 DRUG PROFILE | 18 |
| 1.2.1 Nonclinical pharmacology..... | 18 |
| 1.2.2 Safety pharmacology..... | 19 |
| 1.2.3 Toxicology | 19 |
| 1.2.5 Drug product | 20 |
| 1.2.6 Clinical studies and experience in humans | 20 |
| 2. RATIONALE, OBJECTIVES, AND BENEFIT - RISK ASSESSMENT | 22 |
| 2.1 RATIONALE FOR PERFORMING THE TRIAL | 22 |
| 2.2 TRIAL OBJECTIVES..... | 22 |
| 2.3 BENEFIT - RISK ASSESSMENT..... | 22 |
| 2.3.1 Procedure-related risks | 23 |

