ECGs may be repeated for quality reasons (like alternating current artefacts, muscle movements, electrode dislocation).

All ECGs that are locally printed will be evaluated by the investigator or a designee. For triplicate ECG QTcF values, the mean value will be calculated and interpreted by the investigator or designee. Additional (unscheduled) ECGs may be collected by the investigator for safety reasons. These ECGs are assigned to the prior scheduled time point. Unscheduled ECGs will not be included into the statistical analysis of interval lengths and not evaluated centrally.

For the inclusion or exclusion ([see Section 3.3](#)) of a subject and for the assessment of cardiac safety during the study, the QT and QTcF values generated by the ECG machines or their manual corrections by the investigators will be used. In doubtful cases, ECGs may be sent upfront for centralised evaluation (see below). In this case, these centrally measured results would overrule any other results obtained.

Abnormal findings will be reported as AEs (during the trial) or baseline conditions (at screening) if judged clinically relevant by the investigator. Any ECG abnormalities will be monitored carefully and, if necessary, the subject will be removed from the trial and will receive the appropriate medical treatment. For all volunteers and subjects, for determination of safety and continued inclusion in the study the mean ECG of triplicates will be used for the evaluation.

All ECGs will be stored electronically and transmitted to an ECG core lab
). At minimum, electrocardiograms recorded at the following time points will be evaluated centralized at the core lab:

- Healthy volunteers: Days 1 and 2, and Days 7 and 8 (triplicate ECGs, only)
- CF subjects: All ECGs

The analysis will include the determination of the intervals RR, PR, QRS and QT measured semi-automatically. Other parameters (e.g. cardiac axis) are determined by a validated GE 12-SL-algorithm or equivalent but do not undergo semi-automatic evaluation. All interval measurements in one subject will be performed on the same lead. The intervals will be measured from four cardiac cycles (beats) in lead II. If lead II shows a flat T wave or is not measurable for any reason, lead V5 will be used, or if that lead is not measurable, then lead I will be used. The lead actually used will be reported in the CTR. HR and QTc (QT interval corrected for HR, e.g. QTcF and QTcB) will be determined in-house (see TSAP for details).

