For CF subjects, morphological analyses of the centrally evaluated ECGs (see above) will be performed by a board-certified cardiologist or equivalent. In case of triplicate ECGs recorded at a time point one ECG will be selected randomly for this evaluation. In case additional (unscheduled) ECGs due to safety reasons are recorded at the study site, these ECGs are assigned to the previous scheduled time point, and all ECGs of this time point including the additional ECGs will undergo interpretation. The ECG interpretation will include an overall assessment and a classification of each finding (normal, abnormal clinically relevant, abnormal clinically not relevant, not assessable), in regard to rhythm, conduction and morphological abnormalities, presence of myocardial infarction, ST segment deviations, T-wave morphology (normal, flat, inverted or biphasic) and presence of U-wave (normal and

Proprietary confidential information © 2017 Boehringer Ingelheim International GmbH or one or more of its affiliated companies

abnormal). Abnormalities detected during centralised ECG evaluation will not necessarily qualify as AE.

For blinding arrangements see [section 4.1.5](#).

For quality assurance and control of the measurements, all ECGs of a subject will be subsequently reviewed by the ECG technician supervisor or his/her designee with respect to the overall variance of the measured intervals, in order to detect accidentally switching of leads and/or false subject assignments of the ECGs. After the quality control the fiducial point markings will be reviewed by the cardiologist assigned to the study.

Assessed ECGs will comply with the ICH E14 guidance document and supplements [[R05-2311](#), [R13-0801](#), [R13-4095](#)] as well as the FDA requirements for annotated digital ECGs [[R09-4830](#)].

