6.7 BASELINE, TIME WINDOWS AND CALCULATED VISITS

For endpoints regarding pulmonary function testing (e.g. FEV₁) in-clinic, baseline is defined as the last measurement taken on Day 1 before first study drug administration within each treatment period.

For pulmonary function testing using the home spirometer, baseline is defined as the last measurement taken between Day -7 and -3 before first study drug administration within each treatment period.

For ECG endpoints, baseline is defined as the mean of the last triplicate measurement taken on Day 1 before first study drug administration within each treatment period.

For all other endpoints, baseline is defined as the last measurement before first study drug administration within each trial period. I.e., in case the pre-dose measurement on Day 1 is missing, the measurement between Day -7 and Day -3 will be used as baseline.

Time windows are defined in Section 6.1 of the CTP. Adherence to time windows will be checked at the MQRM.

There will be a centralised evaluation of all 12-lead ECG recordings at the time points identified in Tables 6.7:1 and 6.7:2 for HV and CF subjects, respectively.

Table 6.7: 1 12-lead ECG recordings for HV

Visit	Day	Planned time [hh:mm] (relative to drug administration)	Approximate clock time [hh:mm] of actual day	Study phase	TriPLICATE ECG ¹
1	-21 to -1			Screening	
2	-3 to -1				
	1	-01:00	07:00	Baseline	X
		00:45	08:45	On- treatment	X
		02:00	10:00		X
		04:00	12:00		X
		11:00	19:00		X
	2	23:00	07:00		X
	4	71:00	07:00		
	7	143:00	07:00		X
		144:45	08:45		X
		146:00	10:00		X
		148:00	12:00		X
		155:00	19:00		X
	8	167:00	07:00		X
	16	360:00	08:00		
	23	528:00	08:00		
	30	696:00	08:00		
4	37-44	9999:00	08:00	e.o.s.	

Note: Times are based on Flow Chart I – Healthy Volunteers of CTP Version 3.0 (01 December 2016)

¹ TriPLICATE ECGs on Day 1, 2, 7 and 8 will be evaluated centrally.

Table 6.7: 2 12-lead ECG recordings for CF subjects

Period	Visit	Day	Planned time [hh:mm] (relative to drug administration) CTP Version 8.0(7.0)	According to CTP, Version 7.0 Approximate clock time [hh:mm] of actual day	According to CTP, Version 8.0 Approximate clock time [hh:mm] of actual day	Study phase	Triplet ECG
	1	-21 to -3				Screening	
1/2	2/3	1	-1:00(-02:00)	06:00	7:00	Period Baseline 1/2	X
			00:30	08:30	08:30	On-treatment 1/2	
			04:00	12:00			
			11:00	19:00			
		7	143:00(142:00)	06:00	7:00		
		11	239:00	07:00			
		14	311:00(310:00)	06:00	7:00		
		23	528:00	08:00			

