		30	696:00	08:00	8:00		
		37	864:00	08:00			
	4	44-51	9999:00	08:00	8:00	e.o.s.	

Note: at the end of Visit 2 (period 1), subjects will washout for at least 30 days prior to crossing-over and commencing Day 1 of Visit 3 (period 2). At the end of Visit 3 (period 2), subjects will continue to the end of study visit (Visit 4).

Note: Times are based on Flow Chart II – CF subjects of CTP Version 7.0 (06 September 2017) and Version 8.0 (09 November 2017); all ECGs (single and triplicate) will be evaluated centrally

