The model will include the fixed effects “base 1” as the subject baseline (i.e. the arithmetic mean of the respective period baselines per subject), “base2” as the period baseline, “treatment”, “time”, “Period”, “base1*time” and “base2*time” interaction, “period*time” interaction, and “treatment*time” interaction. Subject is included as a random effect on the intercept. The covariance model for the repeated effect “time” will be unstructured, using the blocking factor ‘subject-by-period’. For each time point, the contrast of the means for “treatment-placebo” will be estimated by the difference in the corresponding adjusted means (Least Squares Means); two-sided 90% CIs based on the t-distribution will also be computed. For each of the above ECG variables, the time profiles of the mean differences to placebo in the changes from baseline and the corresponding 90% CIs will be presented in a figure.

Categorical Endpoints

For the categorical endpoints, frequency tables will be provided.

Categorical endpoints will also include morphological findings that might be attributable to treatment. In particular, new onsets of findings not present at baseline will be explored. A morphological finding observed on treatment that was not reported at baseline will be categorized as a ‘new onset’ of this finding.

For subjects with notable findings, the individual time courses of RR, PR, QRS, QT, HR, QTcF and QTcB of these subjects will be presented in figures.

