9.1 DETAILED DESCRIPTION OF ENDPOINTS FOR ECG

RR, PR, QRS and QT baseline and on-treatment measurements (see [Table 6.7: 1+2](#)) are included in the centralised ECG evaluation. For CF subjects also recordings at screening and end of study are included in addition.

For each single ECG with centralised evaluation, measurements of QT, PR, QRS and preceding RR intervals of four cardiac cycles will be determined and stored in the database as raw data.

QTcF, HR and QTcB will be calculated based on the derivation rules as follows:

From the four cardiac cycles of a single ECG, the HR (measured in beats/min) will be calculated as

$$HR [bpm] = \frac{60\,000}{\overline{RR}}$$

where \overline{RR} is the mean of the four RR intervals (measured in msec).

Similarly, the QT interval corrected for HR according to Fridericia's formula (QTcF) for a single ECG will be derived as

$$QTcF [ms] = \sqrt[3]{\frac{1000}{\overline{RR}}} \overline{QT},$$

where \overline{QT} is the mean of the four QT intervals and \overline{RR} is the mean of the corresponding preceding RR intervals of the four cardiac cycles for this ECG.

Likewise, the HR-corrected QT interval according to Bazett's formula (QTcB) for a single ECG is given by

$$QTcB [ms] = \sqrt[2]{\frac{1000}{\overline{RR}}} \overline{QT}.$$

The PR and QRS values for a single ECG are derived as the means of the PR and QRS values, respectively, of the four cardiac cycles for this ECG.

In case of triple ECGs at a time point, the respective ECG variable will be averaged over the triple ECG measurements at this time point (arithmetic mean). Note that in case of missing values the averaging is simply done for the available values.

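### CF morphology reads one random tracing of the baseline triplicate, so an intermittent finding recorded before dosing on an unread tracing can be tabulated as a new onset; reading all three is a cheap improvement

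*SAP*

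**What the plan says.** **Which CF ECGs are read.** Protocol 5.3.8 states for CF subjects that "morphological analyses of the centrally evaluated ECGs (see above) will be performed" by a cardiologist. Its list of recordings for central evaluation has the entry "CF subjects: All ECGs". The note to SAP Table 6.7: 2 agrees: "all ECGs (single and triplicate) will be evaluated centrally".

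**How triplicates are handled.** Protocol 5.3.8 adds: "In case of triplicate ECGs recorded at a time point one ECG will be selected randomly for this evaluation". Footnote 21 to Flow Chart II says: "Baseline ECG (Day 1) must be in triplicate. All other ECGs to be single". The Day 1 baseline is recorded afresh in Period 2.

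**What counts as new.** SAP 7.8.4 first sets out to explore new onsets of findings that were not present at baseline. Its working rule is different: "A morphological finding observed on treatment that was not reported at baseline will be categorized as a" new onset of that finding.

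**What baseline means.** SAP 6.7 defines the ECG baseline as the mean of the last pre-dose Day 1 triplicate in each period. That suits intervals, but a morphological finding has no mean, and no separate morphology baseline is given. On screening ECGs, SAP 9.1 says: "For CF subjects also recordings at screening and end of study are included in addition". They are not part of the baseline.

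**The concern.** The stated aim concerns what was present before dosing, whereas the rule concerns what was reported. The two differ whenever a finding lies on a pre-dose tracing that nobody read for morphology. In CF the only scheduled triplicate is the baseline, so the random draw sets aside scheduled recordings only there. Every scheduled on-treatment ECG is read.

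A finding that comes and goes, or is borderline, may thus be on file before the first dose of a period and still enter the new-onset table. SAP 7.8.4 presents these as findings that might be attributable to treatment. With 24 CF subjects a few spurious entries would be noticeable, and the tracings that could settle the question would be stored but unread.

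**Working it through.** The plan gives no error rate or expected count for morphology, so there is no figure to reproduce.

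**Inputs from the documents**
- Baseline tracings per period: 3 recorded, 1 read (protocol 5.3.8; Flow Chart II, footnote 21).
- Scheduled on-treatment single ECGs per period, counted from the rows marked "On-treatment 1/2" onwards in SAP Table 6.7: 2, leaving out end of study: 4 under protocol version 8.0 (Day 1 at 0:30, Days 7, 14 and 30) and 9 under version 7.0.
- CF subjects: 24, two periods each.

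**Step 1: the draw alone.** If a finding is on m of the 3 baseline tracings, the random read misses it with probability (3 − m)/3. This is 2/3 for m = 1, 1/3 for m = 2 and 0 for m = 3.

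**Step 2: false new onset with day-to-day variation.** Assumptions, none from the documents: the subject has an intermittent finding and there is no drug effect. The finding is active on a given day with probability a (0.3, 0.6, 0.9) and, if active, visible on each ECG with probability v (0.3, 0.5, 0.8). The baseline and the 0:30 ECG share a day; Days 7, 14 and 30 are independent days. With r baseline tracings read:

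F(r) = [(1 − a) + a(1 − v)^r] − [(1 − a) + a(1 − v)^(r+1)] × (1 − av)^3

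Example, a = 0.6 and v = 0.5:
- F(1) = 0.700 − 0.550 × 0.343 = 0.511
- F(3) = 0.475 − 0.4375 × 0.343 = 0.325

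| a | v | F(1) | F(3) | Share removed by reading all three |
|---|---|---|---|---|
| 0.3 | 0.3 | 0.272 | 0.221 | 19% |
| 0.3 | 0.5 | 0.374 | 0.296 | 21% |
| 0.3 | 0.8 | 0.447 | 0.395 | 12% |
| 0.6 | 0.3 | 0.437 | 0.306 | 30% |
| 0.6 | 0.5 | 0.511 | 0.325 | 36% |
| 0.6 | 0.8 | 0.460 | 0.348 | 24% |
| 0.9 | 0.3 | 0.520 | 0.286 | 45% |
| 0.9 | 0.5 | 0.496 | 0.187 | 62% |
| 0.9 | 0.8 | 0.277 | 0.105 | 62% |

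The draw accounts for 12% to 62% of the false new onsets, and for less than half in 7 of the 9 settings.

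**Step 3: a simpler model.** If all tracings are independent and each shows the finding with probability p, then with k on-treatment ECGs the probability is (1 − p)^r × [1 − (1 − p)^k]. For k = 4:

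| p | One read | Three read |
|---|---|---|
| 0.1 | 0.310 | 0.251 |
| 0.3 | 0.532 | 0.261 |
| 0.5 | 0.469 | 0.117 |
| 0.7 | 0.298 | 0.027 |
| 0.9 | 0.100 | 0.001 |
| 1.0 | 0 | 0 |

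The part due to unread tracings peaks at p = 0.5 among the values tried: 0.469 − 0.117 = 0.352 for k = 4, and 0.374 for k = 9. This model credits the draw with more because it ignores the clustering of findings within a day.

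**The case against.** The strongest defence is that the plan reads one tracing per scheduled time point both before and after dosing, so the draw equalises reading intensity. The excess of false new onsets then comes mainly from setting one pre-dose time point against four, which is inherent in any baseline-referenced definition. On the numbers above this largely stands. It does not answer the narrower point that recordings already on file can contradict the label.

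Several stronger readings are tempting and are not supported:
- **That the rule counts pre-existing findings as new in general.** A finding on all three tracings is always caught. Only intermittent or borderline findings are exposed.
- **That one treatment is favoured.** Under protocol 7.3.4 each CF subject appears in both the active and the placebo group, with the same reading scheme. The documents give no reason to expect a systematic difference.
- **That true signals will be buried.** The documents give no prevalence of intermittent findings. Exclusion criteria 10 and 13 remove subjects with relevant ECG findings, investigators assess the locally printed ECGs, and the central reader classifies each finding by clinical relevance.
- **That the screening ECG should simply join the baseline.** This is a trade-off. A finding seen once at screening would take its recurrence on drug out of the table. Counting Period 1 Day 1 for both periods would also give Period 2 more pre-dose looks than Period 1.

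It is also true that this is a descriptive, further safety criterion, and that over-detection is the cautious direction for a safety screen.

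**Conclusion.** The point holds as a cheap improvement to a descriptive table. The texts together allow a finding recorded before dosing, on a tracing not read, to be tabulated as new. Under the day-level model, the probability per affected subject-period is about 0.27 to 0.52 as planned and about 0.10 to 0.40 with all three tracings read. These figures are conditional on the subject having an intermittent finding and depend on assumed values of a and v. Without a prevalence they cannot be turned into an expected count for the trial.

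The inflation applies to absolute new-onset rates in both treatment columns. The primary TEAE endpoint and the QTcF analyses, which use the triplicate mean as baseline, are not affected.

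A related inconsistency needs settling. Protocol 5.3.8 says in one place that unscheduled ECGs are not evaluated centrally. In another it says that, where an unscheduled safety ECG is taken, all ECGs of that time point are interpreted. The second reading would add further on-treatment looks.

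**What to change.** 1. In protocol 5.3.8, drop the random selection for the CF Day 1 pre-dose baseline and have all three stored tracings read for morphology.
2. In SAP 7.8.4, state that a morphological finding on any pre-dose Day 1 tracing of the period concerned is present at baseline, and that a new onset is a finding seen on treatment in that period and on none of those tracings.
3. Keep in the table, but flag in the listing, any new onset also seen on the centrally read screening ECG or, for Period 2, on the Period 1 Day 1 baseline. The reader can then weigh these without a possible recurrence on drug being removed.
4. Reconcile the two statements in protocol 5.3.8 on central evaluation of unscheduled ECGs.

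The cost is at most 2 unread tracings × 2 periods × 24 subjects = 96 extra morphology reads, plus a short text change and minor programming. No new recordings are needed. Some false new onsets will remain, because one pre-dose time point is still compared with four on treatment; a sentence in the report should say so.

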7.8.5 Others

7.8.5.1 Spirometry

For HV and CF subjects descriptive statistics of spirometry endpoints (FEV₁, FVC, FEV₁/FVC (CF subjects only) and FEF₂₅₋₇₅) over time and their change from baseline will be presented for data obtained in-clinic and with the home spirometer separately (see [Section 6.7](#) for definition of baseline). Time courses of individual subject data and median of FEV₁ and

changes from baseline per dose group will additionally presented graphically separately for data obtained in-clinic and with the home spirometer.

Furthermore, the changes from pre-dose values up to two hours post-dose on Days 1, 7 and 14 will be analysed descriptively.

Clinically relevant findings in spirometry data will be reported as AEs and will be analysed as part of AE analysis.

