Non-clinical studies support repeat-dose clinical trials of up to 4 weeks duration. The relevant systemic findings in the toxicology studies in the rat were changes in serum and urine electrolytes, at delivered doses of 4200 µg/kg/day (4-times higher than the NOAEL dose of 1080 µg/kg) and were consistent with the mode of action of an ENaC antagonist in the kidney. The most sensitive species for these effects was the rat with no relevant effects observed in the dog, even at high doses, on serum or urinary electrolytes. The effects on electrolytes are consistent with the urinary exposure to drug. No other systemic safety findings were observed in either the toxicology or safety pharmacology studies.

Exposure in the present study, for the highest dose of 1800 µg b.i.d (3600 µg/day) is predicted to be approximately 2-fold lower for Cmax and similar exposures for AUC₀₋₂₄ as to the NOAEL values observed in the 4 week rat study. For the highest single dose of 3600ug, less than 1% of parent drug was measured in urine over the first 48 h post dose period (gmean 0.27%, CV 45%).

Off target inhibition of ACh has been observed pre-clinically with augmented effects in non-clinical ACh/MCh challenge guinea pig models. No adverse respiratory effects were detected in the 4-week toxicology studies or in the safety pharmacology studies at doses of up 7,750 µg/ kg in dog or rat. The off target effect is not considered relevant in unchallenged healthy volunteers, and otherwise CF patients. An additional study is planned to assess possible effects in those exposed to acetylcholine or methacholine. Effects on respiratory function will be monitored and are reversible with standard inhaled anticholinergic therapy.

BI 443651 does not present a genotoxic hazard. BI 443651 is considered to be low risk for phototoxicity, based on its absorbance pattern and lack of toxicity in 4-week repeat dose studies.

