7.2 NULL AND ALTERNATIVE HYPOTHESES

Safety and tolerability of 5 groups of 5 different dose levels of BI 443651 are to be determined on the basis of the investigated parameters in comparison to placebo. It is not planned to test any statistical hypotheses with regard to these variables in a confirmatory sense. Instead, they will be described in their entirety and evaluated by descriptive statistical methods.

For both trial parts, confidence intervals will be computed and will have to be interpreted in the perspective of the exploratory character of the study, i.e. confidence intervals are considered as interval estimates for effects.

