7.3.4 Safety analyses

Safety will be assessed for the endpoints and parameters of interest listed in [Section 5.1.1](#) and [5.1.3](#) based on the treated set. Safety analyses (except of ECG data) will be descriptive in nature and will be based on BI standards.

Treatments will be compared in a descriptive way. The control group for HV in the safety evaluation will consist of all placebo treated subjects, regardless of the dose group in which they were treated. For CF, each subject will appear in the active treatment group and the placebo group, due to the cross-over structure. The active treatment groups will be compared to the respective placebo group in a descriptive way. Tabulations of frequencies/proportions will be used for the evaluation of categorical (qualitative) data, and tabulations of descriptive statistics will be used to analyse continuous (quantitative) data.

The analyses will be done by 'randomised treatment'.

Measurements (such as ECG, vital signs, or laboratory parameters) or AEs will be assigned to treatments ([see Section 4.1](#)) based on the actual treatment at the planned time of the measurement or on the recorded time of AE onset (concept of treatment emergent AEs).

Therefore, measurements planned or AEs recorded prior to first intake of trial medication will be assigned to 'screening', those between first trial medication intake until next intake or the end of REP will be assigned to the preceding treatment, and all AEs occurring between the end of REP and next treatment intake or trial termination date respectively will be assigned to 'follow-up'. In case of two or more treatments, the follow-up will be summarized according to the previous treatment. These assignments including the corresponding time intervals will be defined in detail in the TSAP. Please note that AEs occurring after the last per protocol contact but entered before database lock will be reported to drug safety only and will not be captured in the trial database.

Adverse events that start before first drug intake and deteriorate under treatment will also be considered as 'treatment emergent'.

Additionally, further treatment intervals (analysing treatments) may be defined in order to provide summary statistics for time intervals, such as combined treatments, on-treatment totals or periods without treatment effects (such as screening and follow-up intervals).

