7.5 HANDLING OF MISSING DATA

7.5.1 Safety and efficacy

With respect to safety evaluations, it is not planned to impute missing values.

For the assessment of lung function, missing data will not be imputed. The mixed effect model will handle missing data based on a likelihood method under the "missing at random" assumption.

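### CF cross-over: the visible SAP only describes the post-dose FEV1 change, so a cheap within-subject active-minus-placebo estimate with an interval is left unreported

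*SAP*

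**What the plan says.** SAP 7.8.5.1 plans descriptive statistics of FEV1, FVC, FEV1/FVC (CF only) and FEF25-75 over time and as change from baseline, with plots of individual FEV1 time courses and medians. For the acute change after dosing it says: "Furthermore, the changes from pre-dose values up to two hours post-dose on Days 1, 7 and 14 will be analysed descriptively". The section gives no contrast, model or interval.

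This follows Protocol 7.3.4: "Safety analyses (except of ECG data) will be descriptive in nature". The same section has each CF subject appear under both treatments and adds: "The active treatment groups will be compared to the respective placebo group in a descriptive way".

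Three other places bear on the point:

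- SAP 7.8.4 gives CF QTcF, QT and HR a cross-over repeated-measures model, if feasible. It has treatment, time, period, their interactions with time, and subject and period baselines. "Subject is included as a random effect on the intercept". Treatment-minus-placebo LS means with two-sided 90% CIs are reported per time point.
- Protocol 7.5.1, on missing lung-function data, says: "The mixed effect model will handle missing data based on a likelihood method". No lung-function model is specified in the visible text.
- Protocol 7.2 says: "For both trial parts, confidence intervals will be computed", as exploratory interval estimates. It does not say for which variables.

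**The concern.** Each CF subject is measured under active drug and under placebo, so the design supplies a within-subject difference for every post-dose time that both periods share. Separate descriptive columns do not report it. With complete data and 12 subjects per sequence, the difference between column means equals the period-adjusted estimate, but its standard error cannot be obtained from the two SDs because the covariance between periods is not shown. If some subjects lack a period (Protocol 3.3 and 3.3.5 plan 24 and aim for at least 20 completers), the columns also describe different people and a period effect no longer cancels.

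At stake is whether Part 2 can say how large an acute FEV1 fall relative to placebo is compatible with its data. The protocol gives some reason to want that. Section 2.3.2 records: "Off target inhibition of ACh has been observed pre-clinically with augmented effects in non-clinical ACh/MCh challenge guinea pig models". It adds that effects on respiratory function will be monitored. In the current text body plethysmography is done in healthy volunteers only, so spirometry is the main objective airway measure visible in Part 2.

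There is a further reason not to read the active column alone. Protocol 4.2.2.2 lets background therapy be given after the 30-minute spirometry on Days 1 and 14, and permitted therapy includes long-acting bronchodilators. Later changes from pre-dose may mix study drug with background medication. A comparison with the same subject's placebo period removes this as far as background use is the same in both periods.

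**Working it through.** The documents state no precision target, SD or correlation for this measure, so there is no figure of the plan's to reproduce.

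**Inputs from the documents.** n = 24, 12 per sequence (Protocol 7.7); at least 20 completers (Protocol 3.3, 3.3.5); 90% confidence, as for ECG in SAP 7.8.4.

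**Assumed inputs.** SD of the acute FEV1 change 5 percentage points (range 3 to 8); correlation ρ of that change between the two periods 0.5 (range 0.3 to 0.7, with 0 as a check).

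**Formulas for the 90% half-width.**

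- Paired, period-adjusted: t(0.95, n−2) × SD × √(2(1−ρ)/n)
- Two columns treated as independent: t(0.95, 2n−2) × SD × √(2/n)

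**SD 5, ρ 0.5, n 24.**

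- Paired: 1.717 × 5 × √(1/24) = 1.717 × 5 × 0.2041 = 1.75 points
- Unpaired: 1.679 × 5 × √(2/24) = 1.679 × 5 × 0.2887 = 2.42 points
- Ratio: 2.42 / 1.75 = 1.38

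**Effect of the assumed correlation (SD 5, n 24).**

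| ρ | Paired | Unpaired | Unpaired / paired |
|---|---|---|---|
| 0 | 2.48 | 2.42 | 0.98 |
| 0.3 | 2.07 | 2.42 | 1.17 |
| 0.5 | 1.75 | 2.42 | 1.38 |
| 0.7 | 1.36 | 2.42 | 1.78 |

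The ratio does not depend on the SD. Over SD 3 to 8 and ρ 0.3 to 0.7, the paired half-width runs from 0.8 to 3.3 points and the unpaired from 1.5 to 3.9.

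**20 completers, SD 5, ρ 0.5.** Paired: 1.734 × 5 × √(1/20) = 1.94 points.

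**In general units.** The paired 90% half-width is 0.496 within-subject SDs at n = 24 and 0.548 at n = 20. If the within-subject SD were 100 mL (an assumption), that is about 50 mL and 55 mL.

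**The case against.** The strongest reply is that the SAP does what the protocol says. Safety analyses are descriptive, ECG is the named exception, and no hypothesis is tested. That stands: there is no contradiction here, only an estimate not taken.

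Four stronger readings are tempting, and the documents do not support them.

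- A reader might infer that Part 2 yields no active-minus-placebo difference or interval for lung function at all. Protocol 7.5.1 presupposes a lung-function mixed model and Protocol 7.2 promises intervals for both parts. Protocol 7.3.3, SAP 5.3.1 and 6.4 and the opening of SAP 7.6 are not in the public text. Whether that model covers post-dose times cannot be seen.
- A reader might call post-dose FEV1 the trial's direct check on off-target bronchoconstriction. Protocol 2.3.2 does not. It considers the effect not relevant in unchallenged healthy volunteers and CF patients, plans another study for subjects exposed to acetylcholine or methacholine, and monitors respiratory function in general. Protocol 3.2 ties the within-patient comparison to exploratory efficacy, which does not prevent its use for safety.
- A reader might conclude that the pairing is lost. All individual values are listed (Protocol 7.3, SAP 7) and individual FEV1 courses are plotted, so paired differences could be worked out from the report. They are not summarised.
- A reader might want the same for healthy volunteers. Part 1 had its own SAP version, interim lock and unblinded final analysis (Protocol 7.4.1, SAP 4), so a model added now would follow unblinding.

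The precision figures also have limits. The SAP proposes no unpaired interval, so the comparison shows what a reader could derive from two columns. The outcome is already a within-day change, so its correlation across a washout of at least 30 days could be low.

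**Conclusion.** The point holds as a low-cost improvement for the CF part. The visible text plans only a description of the post-dose FEV1 change, so the within-subject difference and its interval go unreported for this safety measure, while the same SAP plans both for CF ECG data. Nothing stated in the plan is wrong.

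The gain is of two kinds. Having an interval at all does not depend on the correlation. The extra precision over unpaired columns does: the unpaired interval is 17%, 38% or 78% wider at assumed correlations of 0.3, 0.5 or 0.7, and at 0 pairing brings nothing. The conclusion is also conditional on the model named in Protocol 7.5.1 not already covering the post-dose change.

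**What to change.** State in SAP 7.8.5.1 whether the lung-function mixed model of Protocol 7.5.1 covers the post-dose FEV1 change. If it does not, add the following for CF subjects, if feasible:

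- **Model.** A cross-over mixed model for the change from same-day pre-dose FEV1, fitted separately by day, with treatment, time, period, treatment-by-time and period-by-time, and a random subject effect. A day with only one post-dose time needs no time terms. Protocol 4.2.2.2 names only Days 1 and 14 as visits with several spirometry tests.
- **Baseline.** Same-day pre-dose FEV1 as the period baseline, plus the subject mean of the two period values. Say this explicitly, because SAP 6.7 defines the in-clinic baseline from Day 1 of each period, which is a different value on Days 7 and 14.
- **Output.** The active-minus-placebo LS mean difference with a two-sided 90% CI at each scheduled post-dose time.
- **Reading.** Treat the 30-minute contrast as the cleanest, because background therapy may follow it on Days 1 and 14.
- **Covariance.** Name a simpler structure in advance in case an unstructured one does not converge with about 24 subjects.

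Keep the descriptive tables, label the results exploratory and make no change for healthy volunteers. SAP 3.0 was written to complete the CF analyses before final database lock, so the change belongs there; if made after lock, report it as post hoc.

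The cost is a paragraph of SAP text and adapted ECG model code, with no new data or subjects. The downsides are a little more analysis work, several exploratory intervals without multiplicity adjustment and possible non-convergence.
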